6.3.1 Sample size

The target enrollment sample size was based on a series of power calculations and incorporates the need to capture seasonal variations in risk factors for pneumonia and in disease incidence, as well as the cost of testing each subject enrolled. The sample size calculations permit sufficient power to undertake site-specific analyses with a reasonable degree of precision, to conduct sub-analyses of pooled data while controlling for age, season, and site, and to support the identification of novel pathogens.

Cases: Small sites (Bamako, Thailand) will enroll all eligible cases. At the other large sites, sampling of cases will be implemented to restrict the target number of PERCH cases to 6300.

Controls: The target number of controls is based on a minimum background enrollment rate of 25 per month (i.e., 600 over 2 years per site) combined with a 1:1 case:control ratio when monthly case enrollment exceeds the minimum control background rate. For large sites, we anticipate that the overall case:control ratio will be approximately 1:1. For small sites, the overall ratio is anticipated to be slightly higher. For Lusaka and Soweto (i.e., sites with high HIV prevalence), an additional HIV+ control group will be added assuming a 1:1 ratio with the number of enrolled HIV+ cases.

Table XIV. Target case and control enrollment by site and total					
Site	Cases	Controls			
		Community	HIV+ controls		
		Controls			
Bamako, Mali	700	900			
Basse, The Gambia	700	900			
Sa Kaeo/Nakhon Phanom, Thailand	500	600			
Soweto/Johannesburg, South Africa	1200	800	400		
Dhaka, Bangladesh	1200	1200			
Kilifi, Kenya	1200	1200			
Lusaka, Zambia	800	850	350		
Total	6300	7	200		

While PERCH has set a target of 6300 cases to be enrolled, the number actually available may range from 5000-7000. This is due either to losses in data for analysis or higher than projected numbers of cases consenting at some sites. Losses may result from inability to collect and test all specimens, ineligibility due to severe pneumonia signs resolving upon administration of bronchodilators, changes in procedures over time that result in excluding some cases from analysis, and because some sites may not be prepared to start in Jan 2011 (due to minor site capacity development or IRB processes) and thus may not achieve a full 2 years enrollment before the study ends. To account for these potential losses, a low (70%) estimate is provided below.

Table XV. Target number of cases						
	Target	70% of target				
Site	Total cases	Total cases				
Bamako, Mali	700	490				
Basse, The Gambia	700	490				
Sa Kaeo/Nakhon Phanom, Thailand	500	350				
Soweto/Johannesburg, South Africa	1200	840				
Dhaka, Bangladesh	1200	840				
Kilifi, Kenya	1200	840				
Lusaka, Zambia	800	560				
Total	6300	4410				

HIV-infected cases and controls: Four of the 7 sites have measureable numbers of HIV-infected cases that could be included in an HIV-infected sub-group analysis, either pooled or as a site-specific analysis at the two largest sites. Since HIV status is associated with pathogen infection (i.e., higher carriage in HIV+ than HIV-), and with disease (e.g., higher rates of invasive pneumococcal disease and PCP in HIV+), stratifying analyses by HIV status is desired. Table XV describes the projected number of cases and controls enrolled with HIV. At the two sites with high HIV prevalence (Johannesburg and Lusaka), a second control group of HIV-infected children will be recruited from HIV patient support centers to ensure a sufficient number of HIV+ controls.

Tab	Table XVI. Estimated number of HIV+ cases and controls available in PERCH, by site						
	HIV+	Н	IV+ controls				
Site	cases	community	controls	Total	Assumptions re: HIV prevalence in		
		controls	recruited		cases and community controls		
			from PSCs				
Kilifi	84	24	0	24	7% of cases are HIV+. Assume 2% of		
					children in community are HIV+.		
Soweto	400	40	400	440	5% of U5 are infected and 35% of		
					hosp sev pn are HIV+		
Bamako	63	15	0	15	9% of OP Spn bacteremia were HIV+		
					vs 1.7% controls		
Lusaka	400	50	350	400	30% of children with access to care		
					are HIV+ (assume 50% of sev pn and		
					20% of controls are HIV+)		
Total	947	129	750	879			

Severe versus very severe cases: Because the proportion of very severe pneumonia cases is small compared to severe pneumonia cases, indiscriminant selection may result in insufficient enrollment of very severe pneumonia cases. Therefore, at most sites, all very severe cases will

be invited to participate. At the largest sites, an equal number of severe and very severe cases will be targeted by applying a sampling ratio that is higher for very severe cases.

Table XVII. Target number of severe and very severe pneumonia cases						
	Target		70% of target			
Site	Severe	Very severe	Severe	Very severe		
Bamako, Mali	525	175	368	123		
Basse, The Gambia	526	174	368	122		
Sa Kaeo/Nakhon Phanom, Thailand	400	100	280	70		
Soweto/Johannesburg, South Africa	660	540	462	378		
Dhaka, Bangladesh	900	300	630	210		
Kilifi, Kenya	840	360	588	252		
Lusaka, Zambia	400	400	280	280		
Total	4251	2049	2976	1434		

Number of cases available by age group: Assuming the age distribution of cases is 50% 1-11m, 30% 12-23m, and 20% 24-59m, the estimated number of cases by age group per site and overall are provided in Table XVII.

Table XVII. Estimated number of severe and very severe pneumonia cases by age

	Target			70% of target		
Site	Total	Severe	Very	Total	Severe	Very
	cases		severe	cases		severe
Bamako, Mali	350	263	88	245	184	61
Basse, The Gambia	350	263	87	245	184	61
Sa Kaeo/Nakhon	250	200	50	175	140	35
Phanom, Thailand						
Soweto/Johannesburg,	600	330	270	420	231	189
South Africa						
Dhaka, Bangladesh	600	450	150	420	315	105
Kilifi, Kenya	600	420	180	420	294	126
Lusaka, Zambia	400	200	200	280	140	140
Total	3150	2126	1025	2205	1488	717

(A) age 28 days-11 months

(B) age 12-23 months

	Target			70% of Target		
Site	Total	Severe	Very	Total	Severe	Very
	cases		severe	cases		severe
Bamako, Mali	210	158	53	147	110	37
Basse, The Gambia	210	158	52	147	110	37
Sa Kaeo/Nakhon	150	120	30	105	84	21

Phanom, Thailand						
Soweto/Johannesburg,	360	198	162	252	139	113
South Africa						
Dhaka, Bangladesh	360	270	90	252	189	63
Kilifi, Kenya	360	252	108	252	176	76
Lusaka, Zambia	240	120	120	168	84	84
Total	1890	1275	615	1323	893	430

(C) age 24-59 months

	Target			70% of Target		
Site	Total	Severe	Very	Total	Severe	Very
	cases		severe	cases		severe
Bamako, Mali	140	105	35	98	73	25
Basse, The Gambia	140	105	35	98	74	24
Sa Kaeo/Nakhon	100	80	20	70	56	14
Phanom, Thailand						
Soweto/Johannesburg,	240	132	108	168	92	76
South Africa						
Dhaka, Bangladesh	240	180	60	168	126	42
Kilifi, Kenya	240	168	72	168	118	50
Lusaka, Zambia	160	80	80	112	56	56
Total	1260	850	410	882	595	287

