4.3 Control selection

Controls selected from the community will be enrolled approximately on a 1:1 basis to cases, with a minimum of 25 controls enrolled per month. Parents/guardians of control subjects will be compensated according to the routine practice at each site. Local practices and IRB guidelines will govern the amount and type of compensation; the amount offered will not be so high as to induce someone to participate in the study. Food and transportation reimbursement are examples of the types of compensation that could be provided by the sites. Specific details will be included in site specific appendices. Basic demographic information on eligible children

Version 6.0_15Nov2013

not enrolled, including the reason for not enrolling, will be collected and used to compare enrolled and non-enrolled children.

[figure not shown]
Table VII presents an overview of the control evaluation schedule of activities. Details for each time point are described in sub-section 4.4 below.

Table VII. Overview of Control Study Evaluations							
	Follow-up time point						
Activity	Day screened	Day enrolled*					
Log of assessed children	Х						
Eligibility assessment	Х						
Enrollment/Consenting		Х					
Specimen Collection:							
Blood		Х					
 Nasal and throat swabs 		Х					
Urine		Х					
Demographic, clinical history and risk factor assessment		x					
Limited clinical assessment (i.e. respiratory signs, respiratory rate, neurological signs, rash, temperature)		X					

*May be the same day of screening for children enrolled at home.

Controls will be selected from the community from which the cases came (but not matched by geographic location). Approximately 1 control per case will be enrolled. PERCH sites will recruit a minimum of 25 control patients per month. In months where the number of cases exceeds 25, sites will enroll controls in an additional 1:1: ratio to achieve the same number as cases enrolled that month.

Figure V. Illustration of control selection rates relative to the case enrollment rates

In the two sites with high HIV prevalence (Zambia and South Africa), a separate control enrollment strategy will be deployed in addition to the above strategy to capture a second group of HIV-infected controls for the etiologic analysis (see section 4.4.6).

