6.3.3 Power

Key analyses addressed in this section include determining:

- i. the association of pneumonia with detection of pathogens in nasopharyngeal specimens
- ii. the statistical precision of estimates for individual pathogen prevalence
- iii. the risk factors associated with pneumonia
- iv. the background prevalence of risk factors in the study population

Case-control analyses will be used to address (i) and (iii), and case-series analyses will be used to address (ii) and (iv).

For case-control analyses, an equal number of cases and controls is assumed. Analyses will be conducted both by site and pooled across sites. Site-specific and between-site analyses will illuminate which etiologies are common globally and which vary in importance depending on geography and local epidemiologic settings.

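### Table XIV's Soweto target of 800 community controls for 1200 cases cannot come from the written control rule, which gives at least 1200, with the HIV-infected controls on top

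*Protocol*

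**What the plan says.** Section 4.3 (Control selection) sets the community rule: "Controls selected from the community will be enrolled approximately on a 1:1 basis to cases, with a minimum of 25 controls enrolled per month". For months with more than 25 cases it adds that "sites will enroll controls in an additional 1:1: ratio to achieve the same number as cases enrolled that month". It then describes a separate strategy for HIV-infected controls in Zambia and South Africa, on top of the community strategy and intended for the etiologic analysis.

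Section 6.3.1 (Sample size, Controls) repeats the rule: a floor of 25 a month, which it equates to 600 per site over two years, "combined with a 1:1 case:control ratio when monthly case enrollment exceeds the minimum control background rate". It expects the following at the bigger sites: "For large sites, we anticipate that the overall case:control ratio will be approximately 1:1". For Lusaka and Soweto it says that "an additional HIV+ control group will be added assuming a 1:1 ratio with the number of enrolled HIV+ cases".

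Table XIV, in the order cases, community controls, HIV-infected controls, then reads "Soweto/Johannesburg, South Africa 1200 800 400" and "Lusaka, Zambia 800 850 350". Dhaka and Kilifi, the other two sites with 1200 cases, each have 1200 community controls. The table's control total is 7200.

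On power, section 6.3.3 says: "For case-control analyses, an equal number of cases and controls is assumed". That sentence covers both the pathogen comparison and the risk-factor comparison.

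**The concern.** The text makes the HIV-infected group an addition to a community series that is never smaller than the case series. The Soweto row looks as though the 400 HIV-infected controls were instead taken out of 1200, leaving 800. The Lusaka row, governed by the same sentence, adds them on top.

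Two things are at stake. The first is operational. At an even 50 cases a month, a team following section 4.3 would reach 800 community controls in month 16 of 24. Stopping there would leave eight months without community controls and break the matching by month in section 4.3.7. Spreading 800 over 24 months means about 33 a month against 50 cases, which section 4.3 does not allow. The second is statistical. Any Soweto analysis that uses all cases and only community controls would have two controls for every three cases, while the power section assumes one for one.

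**Working it through.** **Inputs.** Cases, community controls and HIV-infected controls by site come from Table XIV. HIV-infected counts come from Table XVI. The control rule comes from sections 4.3 and 6.3.1. Two-sided alpha 0.01 and an odds ratio of 2.0 come from section 6.3.3.1. Equal allocation comes from section 6.3.3.

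**Table total.** Community: 900 + 900 + 600 + 800 + 1200 + 1200 + 850 = 6450. HIV-infected: 400 + 350 = 750. Sum 7200, as printed. The addition is right; the question is the Soweto cell.

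**What the rule gives.** Community controls are the sum over 24 months of max(25, cases in the month). Each term is at least that month's cases, so the sum cannot be below the case total, whatever the seasonality. Soweto averages 1200/24 = 50 cases a month, so the rule gives at least 1200 community controls. The table has 800, a ratio of 800/1200 = 0.67 and a shortfall of at least 400. With the other cells unchanged, the community total becomes 6450 + 400 = 6850, and all controls 6850 + 750 = 7600.

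**Can one reading of the rule fit both HIV sites?**

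| Reading | Soweto community | Lusaka community |
|---|---|---|
| HIV-infected controls added on top | at least 1200 | at least 800 |
| HIV-infected controls counted inside 1:1 | 1200 − 400 = 800 | 800 − 350 = 450, lifted to 600 by the floor (25 × 24) |
| Table XIV | 800 | 850 |

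The first reading fits Lusaka only, the second Soweto only.

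**Is 800 a misprint?** Table XVI expects 40 HIV-infected children among the Soweto community controls at 5% prevalence. 0.05 × 800 = 40, whereas 0.05 × 1200 = 60. So 800 was carried through deliberately.

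**HIV strata at Soweto as tabulated.** HIV-infected: 400 cases against 40 + 400 = 440 controls. HIV-uninfected: 1200 − 400 = 800 cases against 800 − 40 = 760 controls. Both are close to 1:1.

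**Power.** For case prevalence p1 and odds ratio 2, the control prevalence is p0 = o/(1 + o), with o = p1/[2(1 − p1)]. Power = Φ{[(p1 − p0) − 2.576·√(p̄(1 − p̄)(1/n1 + 1/n0))] / √(p1(1 − p1)/n1 + p0(1 − p0)/n0)}, where p̄ is the prevalence over both groups combined.

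The protocol's own claim is checked first: at least 80% at every site for 15% case prevalence. The smallest site, taken as 500:500, gives 79.9%, so the claim reproduces to rounding.

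Example at p1 = 0.06: o = 0.0319 and p0 = 0.0309.
- 1200:1200: (0.02907 − 0.02191)/0.00848 = 0.845, power 80.1%.
- 1200:800: (0.02907 − 0.02522)/0.00919 = 0.419, power 66.2%.

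| Case prevalence | 1200:1200 | 1200:800 | HIV-uninfected 800:760 | HIV-infected 400:440 |
|---|---|---|---|---|
| 15% | 99.7% | 98.4% | 95.4% | 71.3% |
| 10% | 96.4% | 90.4% | 82.8% | 51.0% |
| 6% | 80.1% | 66.2% | 56.8% | 29.7% |

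At 70% of target, 840:560 still gives 91.2% at 15% prevalence.

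**The case against.** A reader might infer that Soweto falls 400 controls short of the equal-numbers assumption behind the power section. The documents do not support that in general. Section 6.3.3 speaks of equal cases and controls, not of community controls, and Soweto has 800 + 400 = 1200 controls for 1200 cases. Section 4.3.4 says that an unconfounded pathogen comparison sets HIV-infected cases against HIV-infected controls, and both HIV strata are near 1:1. Comparing all cases with mostly uninfected community controls is not the pathogen comparison that the protocol prefers. No stated site-level power figure fails either: the text claims 80% at 15% prevalence, and 1200:800 gives 98.4%. The text makes no such claim at 6%, where sites of 500 or 700 per group would have only 36% or 51%. All of this stands.

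It can also be said that Table XIV is a planning target, that the ratios are described as approximate, and that Soweto, Lusaka, Dhaka and Kilifi each total exactly 1200 controls, which suggests a common per-site total. But a ratio of 0.67 is not approximately 1:1, and no passage states a per-site total as the rule.

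What the objection leaves in place is the mismatch itself, together with the analyses that use community controls alone. Section 4.3 reserves the HIV-infected group for the etiologic analysis. Those children are recruited from HIV support centers because they are infected, so they cannot stand for the source population in a risk-factor analysis, least of all for HIV itself. The risk-factor power text (6.3.3.3) nevertheless refers back to the equal-numbers calculation.

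**Conclusion.** The Soweto row of Table XIV contradicts sections 4.3 and 6.3.1. The written rule gives at least 1200 community controls where the table has 800, and at least 7600 controls overall where the table has 7200. The 7600 is a lower bound for Soweto combined with unchanged table values elsewhere. The table is consistent within itself, so this is a conflict between text and table, not an addition error. No single reading of the written rule produces both the Soweto and the Lusaka rows.

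The consequence for power is real but confined. It applies to Soweto analyses of all cases against community controls alone: 96.4% falls to 90.4% at 10% case prevalence, and 80.1% to 66.2% at 6%, for an odds ratio of 2.0 at two-sided alpha 0.01. These figures assume an unadjusted two-proportion test and full recruitment. It would be wrong to conclude that the site is underpowered against what the protocol promises, or that the HIV-stratified pathogen comparisons are unbalanced. Nor do the documents show what was budgeted for controls, so nothing can be said about an unfunded shortfall. The mismatch should be corrected because it concerns an enrolment target that its own rule cannot generate.

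**What to change.** Choose one of two corrections.

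**Keep 800.** State in 4.3 and 6.3.1 that at Soweto the HIV-infected controls count toward the 1:1 total. Present this as an explicit site exception, because at Lusaka they are additional. Give Soweto a matching monthly rate for community controls, about two per three cases and averaging 800/24 ≈ 33 a month, so that roughly 800 are spread over all 24 months and the matching by month survives. In 6.3.3, give Soweto power at 1200:800 for analyses against community controls and at about 800:760 and 400:440 for the HIV strata. The cost is wording and a less favourable stated power; no additional child is enrolled beyond Table XIV.

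**Keep the written rule.** Correct Table XIV to 1200 community controls at Soweto and 7600 controls in all. Update Table XVI for Soweto from 40 to 60 HIV-infected community controls and from 440 to 460 HIV-infected controls, and its column totals from 129 to 149 and from 879 to 899. The cost is 400 more controls to enrol and test than the table now shows; the equal-numbers assumption then holds for the Soweto risk-factor analyses as well.

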4.3.4 Rationale for HIV infected controls

Because of the very increased risk of pneumonia among HIV-infected children, it is expected that the cases will be disproportionately HIV-infected compared to the community. In the sites with high HIV prevalence (i.e. Zambia and South Africa), this might result in up to half of cases being HIV-infected. The community prevalence of HIV infection in children < 5 years, even in these high prevalence areas, will likely be <5%. Therefore, this will lead to an over-representation of HIV-infected cases compared with controls. This is the principle upon which to estimate the magnitude of the association between HIV and pneumonia. However, it is expected that the etiologic spectrum of respiratory pathogens will differ in HIV-infected children as will the pathogens colonizing the nasopharynx. An unconfounded analysis of the causal association between nasopharyngeal infection and pneumonia needs to compare HIV-infected cases with HIV-infected controls. To achieve sufficient numbers of HIV-infected controls to enable this comparison, a separate sampling strategy has been designed to enroll HIV-infected controls in these two sites.

HIV-infected controls will be enrolled from HIV patient support centers (PSC) serving the hospital catchment population. PSCs include ARV/ART clinics. We considered enrolling

hospitalized HIV-infected control subjects but rejected this option because of a 2-3 day lag-time in making the HIV diagnosis, by which time the naso/oropharyngeal flora will likely have become altered with nosocomially –acquired pathogens. Secondly, infants who are HIV-infected and admitted with non-pneumonia diagnoses have been difficult to find in South Africa due to improved prevention-of –mother –to-child-transmission and lower prevalence of HIV among newborns.

In Zambia and South Africa, HIV-infected controls will be enrolled in a 1:1 ratio with HIVinfected PERCH cases using the same age frequency matching approach described in section 4.3.7.

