Site	Total Severe* Very severe				
	cases				
Bamako, Mali	700	525	175		
Basse, The Gambia	1170	1016	154		
Sa Kaeo/Nakhon	500	400	100		
Phanom, Thailand					
Soweto/Johannesburg,	2000	1460	540		
South Africa					
Dhaka, Bangladesh	3000	2250	750		

Kilifi, Kenya	1800	1440	360
Lusaka, Zambia	3400	2000	1400
Total	12570	9091	3479

*For sites with unknown ratio of severe to very severe, 25% very severe was assumed.

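### The severity targets in Table XVII break the protocol's own rule at Dhaka (900/300, no oversampling of very severe cases) and exceed the listed supply at Basse (174 against 154); control counts at Soweto and Lusaka also need reconciling.

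*Protocol*

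**What the plan says.** **Severity rule.** Protocol 4.1.3 aims for equal numbers of severe and very severe cases, obtained by sampling very severe cases at a higher rate, and expects most sites to enrol every very severe case. Section 6.3.1 repeats this for the biggest sites: "At the largest sites, an equal number of severe and very severe cases will be targeted". The means is again a higher selection rate in the very severe stratum.

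**Severity figures.** Table XIII (6.3) estimates the cases available over two years, and Table XVII (6.3.1, severe versus very severe) sets the targets. At "Basse, The Gambia", 154 very severe cases are listed as available and 174 are targeted. At Dhaka, 750 are listed and 300 targeted. A footnote to Table XIII says that 25% very severe was assumed wherever a site's ratio was unknown.

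**Control rule.** Section 4.3 asks for about one community control per case, at least 25 a month, and in months with more than 25 cases a 1:1 "ratio to achieve the same number as cases enrolled that month". For Zambia and South Africa, "a separate control enrollment strategy will be deployed in addition to the above strategy". Section 6.3.1 also calls the HIV-infected group additional and sets it 1:1 with enrolled HIV-infected cases.

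**Control figures.** Table XIV gives "Soweto/Johannesburg, South Africa" 1200 cases, 800 community controls and 400 HIV-infected controls. Lusaka has 800, 850 and 350. Table XVI gives Lusaka 50 HIV-infected community controls, with the note that "20% of controls are HIV"-infected. Section 4.3.4 says that community prevalence, "even in these high prevalence areas, will likely be <5" per cent.

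**The concern.** Very severe cases are oversampled because the study is about pathogens that cause fatal pneumonia, and very severe disease is the nearest observable stand-in. Section 6.3.1 itself warns that unselective sampling may yield too few of them. A site recruiting to the Dhaka row would do what that warning describes: take the same fraction of both strata and leave 450 of the 750 listed very severe cases (750 − 300) unenrolled. Dhaka has one of the three largest case targets, so it has the most room to gain.

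The Basse row asks for more very severe cases than the protocol's own estimate, and the error passes into the tables by age. The control rows matter for a different reason. At Soweto, field staff cannot tell from the protocol whether HIV-infected children from the support centres count towards the 1:1 ratio, and section 6.3.3 assumes equal numbers of cases and controls.

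**Working it through.** **1. The plan's totals reproduce.**

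- Table XVII: severe 525+526+400+660+900+840+400 = 4251; very severe 175+174+100+540+300+360+400 = 2049; sum 6300.
- Table XIV: community controls 900+900+600+800+1200+1200+850 = 6450; plus 400+350 = 750; sum 7200.

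The tables add up, so the conflict is between rows and rules.

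**2. Sampling fractions at the sites that sample** (target ÷ available, Table XVII ÷ Table XIII).

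| Site | Severe | Very severe |
|---|---|---|
| Basse | 526/1016 = 52% | 174/154 = 113% |
| Soweto | 660/1460 = 45% | 540/540 = 100% |
| Dhaka | 900/2250 = 40% | 300/750 = 40% |
| Kilifi | 840/1440 = 58% | 360/360 = 100% |
| Lusaka | 400/2000 = 20% | 400/1400 = 29% |

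Soweto and Kilifi take every very severe case and so cannot reach equality. Lusaka reaches it at 400/400. Dhaka neither takes all its very severe cases nor reaches equal numbers, and it has no listed shortage: half of 1200 is 600, below 750.

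**3. Basse.** 174/700 = 24.9%, while the site's own share is 154/1170 = 13.2%. The target looks like the 25% default applied to a site that has its own figure. The age tables repeat it: 87 + 52 + 35 = 174.

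**4. Totals after correction.** Very severe 2049 − 20 + 300 = 2329; severe 4251 + 20 − 300 = 3971; sum 6300.

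**5. Power at Dhaka, by severity stratum.** The odds ratio of 2 and two-sided alpha of 0.01 come from 6.3.3.1, and the 1200 controls from Table XIV. The 10% case prevalence is my choice. Then p1 = 0.10 and p0 = (0.1111/2)/(1 + 0.1111/2) = 0.0526. Power = Φ[(p1 − p0 − 2.576·s0)/s1], where s0 is the standard error under the pooled proportion and s1 the unpooled one.

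- 300 very severe: s0 = 0.01558, s1 = 0.01848, power 65%.
- 600 of either stratum: s0 = 0.01262, s1 = 0.01384, power 86%.
- 900 severe: s0 = 0.01147, s1 = 0.01190, power 93%.

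**6. How far Dhaka rests on the 25% share.** 750/3000 is exactly 25%. A target of 600 needs a true share of at least 600/3000 = 20%. At the lowest share listed for any site (Basse, 13.2%), Dhaka would have about 3000 × 154/1170 = 395 very severe cases, still more than 300.

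**7. Soweto.** 1200/24 = 50 cases a month, above the minimum of 25, so the community rule implies about 1200 community controls. The row gives 800/1200 = 0.67 per case. It reaches (800 + 400)/1200 = 1.00 only if HIV-infected controls are counted. Lusaka meets 1:1 with community controls alone: 850/800 = 1.06.

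**8. Table XVI, HIV-infected community controls.** Kilifi 2% × 1200 = 24, Soweto 5% × 800 = 40 and Bamako 1.7% × 900 ≈ 15 all match. Lusaka does not: 20% × 850 = 170, against 50 listed. The listed 50 is 50/850 = 5.9%, and 5% would be about 42.

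**The case against.** **Dhaka.** The protocol does not define which sites are largest, its 750 may rest on the default share, and no power statement in 6.3.3 depends on the Dhaka split. Moving to 600/600 also costs power in severe cases. All of this stands and limits the size of the point. It does not rescue the row: Dhaka is second by available cases and joint first by target, and the row applies no higher ratio at all.

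**Basse.** A reader might infer that the target cannot be met. The documents do not support that. Table XIII is an estimate, the text calls it conservative, and 6.3.1 allows for more cases than projected at some sites. The gap is 20 cases.

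**Soweto.** A reader might infer that the site is plainly 400 controls short, loses monthly matching and loses power. The sentence in 6.3.1 expecting an overall ratio near 1:1 at large sites can be met by 800 + 400. Table XIV is a two-year projection, while enrolment follows the monthly rule. A power comparison of 1200 cases with 800 or 1200 community controls mixes HIV strata that 4.3.4 says must be compared within HIV status. By stratum, Tables XIV and XVI give about 800 uninfected cases (1200 − 400) to 760 uninfected controls (800 − 40), and 400 infected cases to 440 infected controls, both close to 1:1. The protocol's site-level claim (80% power at 15% case prevalence) still holds, with 98% at 1200:800. What remains is a conflict of wording and a row treated differently from Lusaka's.

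**Lusaka.** It is tempting to recompute the 350 support-centre target from a corrected community prevalence, since 400 − 50 = 350. The protocol never states that subtraction, and Soweto's row does not use it (400 recruited plus 40). The written rule is 1:1 with HIV-infected cases.

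**Conclusion.** The point holds for the severity targets. Dhaka's 900/300 contradicts 4.1.3 and 6.3.1, and Basse's 174 contradicts Table XIII. Correcting both gives 280 more very severe cases (2,329 against 2,049, about 14%) at the same 6300. Nearly all of this is Dhaka; Basse is a minor slip. Power in Dhaka's very severe stratum gains about 21 percentage points and power in its severe stratum loses about 7, under the assumptions shown. The full gain assumes a true very severe share at Dhaka of at least 20%.

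Soweto's control counts and Lusaka's HIV figure are secondary inconsistencies to reconcile. Neither overturns a stated power claim. The corrections should be made, but the pooled design does not depend on them.

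**What to change.** 1. In Table XVII set Dhaka to 600/600, or as near as the confirmed supply of very severe cases allows, and say whether its 25% share is observed or assumed. Set Basse to 546/154. Recompute the totals, the 70% columns and the age tables. State which sites count as largest.
2. For Soweto, choose one reading. Either list 1200 community plus 400 HIV-infected controls, which raises the control total from 7200 to 7600; or state in 4.3 and 6.3.1 that HIV-infected controls count towards 1:1, and replace the equal-numbers assumption in 6.3.3 for that site with the actual allocation, preferably by HIV stratum.
3. For Lusaka, correct either the 20% assumption or the figure of 50 in Table XVI, and reconcile the 350 support-centre target with the written rule of 1:1 with the 400 HIV-infected cases.

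The severity correction adds no cases. The Soweto point can be settled in text alone; only the first option adds controls (400). The Lusaka point is a corrected note, plus up to 50 further support-centre controls if the written 1:1 rule is kept (400 − 350).
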